2.2 SECONDARY OBJECTIVE(S)

The secondary objectives of this study are:

- 1. To investigate the tolerability and safety of Enterosgel®
- 2. To investigate the impact of Enterosgel® on:
 - a) stool frequency
 - b) duration of other symptoms and signs of intestinal infection (i.e. fever, nausea, vomiting, abdominal pain)
 - c) diarrhoea complications resulting in hospitalisation, Accident & Emergency room attendance, nurse/GP home visit or unscheduled visit to the medical practice

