3.2 STUDY OUTCOMES

3.2.1 Primary Outcome

Duration of diarrhoea defined as time (hours) from randomisation to first nonwatery stool (soft or firm)

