3.2.2 Secondary Outcome(s)

 Duration of diarrhoea defined as time (hours) from randomisation to last watery stool

Stop Enterosgel if diarrhoea resolved

- 2. Percentage of patients with diarrhoea resolved on Day 3 (i.e. first soft or firm stool recorded on Day 0-3)
- 3. Stool frequency defined as average number of stools/day from randomisation to first soft or firm stool
- 4. Tolerance and safety of Enterosgel® (assessed via Adverse Event (AE) reporting from start of treatment until end of Day 7)
- Percentage of patients with diarrhoea-related complications resulting in hospitalisation, Accident & Emergency department visit, nurse/GP home visit or unscheduled visit to the medical practice from randomisation until end of Day 7
- 6. Duration (days) of the following from randomisation:
 - a) Nausea
 - b) Vomiting
 - c) High body temperature defined as ≥38°C
 - d) Abdominal pain

Patient diary is the data source for all efficacy outcomes. Any AEs related to taking study treatment(s) should also be recorded in the patient diary. Any diarrhoea-related complications resulting in hospitalisation, Accident & Emergency department visit, nurse/GP home visit or unscheduled visit to the medical practice, should be reported by the patient during follow-up calls and recorded by the nurse in practice medical notes and the eCRF.

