The research nurse or GP will then randomise the patient to the intervention group using a computerised randomisation tool. Patients randomised to the Interventional group will be provided with a sufficient amount of Enterosgel® for 5-7 days of treatment and should take Enterosgel® as instructed in the study-specific instructions which will be provided to them (**Appendix A**). Patients randomised to the Control group will not receive any treatment in addition to the standard of care ORS treatment. The details of prescribed ORS treatment and any dietary recommendations will be recorded in the eCRF.

All patients will be provided with a patient diary (**Appendix C**) to record:

- 1. stool times and consistency
- 2. diarrhoea medication use
- 3. other symptoms (fever, nausea, vomiting etc.)
- 4. any AEs

Patients should fill in the patient diary daily from Day 0 until end of Day 7.

Patients will be asked to take a stool sample on the same day at home in a provided clean container. Patients in the Interventional Group should take the stool sample before taking the first Enterosgel® dose. ORS treatment can be started before taking the stool sample. The sample should be taken to the medical practice by the patient or a family member/friend. It will then be delivered to a local laboratory to test for the presence of rotavirus and diarrhoea causing bacteria (i.e.

Campylobacter, Clostridium difficile, Escherichia coli, Salmonella enterica, Shigella), in order to identify the likely cause of the episode. If there is a reason to suspect norovirus infection (i.e. outbreak), this will also be tested for. Patients who have recently travelled abroad will be additionally tested for *Pseudomonas* and *Vibrio cholerae*. A stool sample will only be collected in baseline and the results will be summarised in baseline characteristics.

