8 STATISTICS

8.1 POWER CALCULATION

The power calculation for this study is based on demonstrating superiority of the Interventional Group on the primary outcome, duration (days) of diarrhoea. Power was calculated using an online power calculator for continuous outcome superiority trial (Sealed Envelope Ltd. 2012. Available from: https://www.sealedenvelope.com/power/continuous-superiority/).

In line with some previous studies, we assumed a standard deviation for the duration of diarrhoea of 1.3 days (14,15). In order to detect an average decrease of 1 day in the duration of diarrhoea in the Interventional group compared with the Control group, 36 patients in each group are required for 90% power to demonstrate superiority at 5% significance level. Accounting for a combined patient withdrawal and missing data rate of 30%, 52 patients will need to be randomised into each group. Therefore, the total number of patients enrolled will be 104.

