8.2 STATISTICAL ANALYSES

A CONSORT flow diagram will show the progress through the parallel randomised trial (that is, enrollment, intervention allocation, follow-up, and data analysis). The baseline characteristics of the groups will be summarised as mean (standard deviation) or n (%). The baseline characteristics will not be compared statistically, in line with CONSORT.

Primary analysis will be conducted on an intention-to-treat basis. The primary outcome will be summarised as mean (standard deviation). The Interventional

group and Control group will be compared using a t-test or Mann Whitney test, as appropriate. A generalised linear model will undertaken to control for an potentially confounding variables, e.g. age and gender.

Secondary outcomes will be summarised as mean (standard deviation) or n(%) median (interquartile range). The Interventional group and Control group will be compared using a t-test or Mann Whitney test for continuous data (e.g. duration of nausea, vomiting and fever) and chi-square tests for categorical data (e.g. complication rate).

A p-value of <0.05 will be considered to indicate statistical significance and all analyses will be undertaken on STATA.

A 30% drop out has been taken into account in the sample size calculation for the primary analysis to allow for missing data. The extent and reasons for missing data will be reported and investigated to see whether the data is missing at random. This will inform which methods to handle missing data will be employed. Sensitivity analyses will be performed as appropriate.

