15 APPENDICES

APPENDIX A: ENTEROSGEL® STUDY USE INSTRUCTIONS

Randomised, multi-centre study to assess efficacy, tolerability and safety of Enterosgel® in treatment of acute diarrhoea in adults

Enterosgel® use instructions for research participants

IMPORTANT:

- Stop taking Enterosgel® if you did not have any bowel movements for 2 days at any stage of the study
- Mix every dose of Enterosgel® in 100-200 ml of room temperature water
- Please leave at least 1 hour between taking Enterosgel® and any other medication or meals

Day 0 (today):

First dose (as soon as possible): 2 tablespoons or 2 sachets of Enterosgel®

After the first dose: 1 tablespoon or 1 sachet of Enterosgel® after every bowel movement up to a total of 6 times and at least 3 times a day

Day 1:

If you have loose stool more than once a day:

1 tablespoon or 1 sachet of Enterosgel® after every bowel movement up to a total of 6 times and at least 3 times a day

If you don't have loose stool or have it just once a day:

1 tablespoon or 1 sachet of Enterosgel® 3 times a day

Days 2, 3, 4 and 5:

If you have loose stool more than once a day:

1 tablespoon or 1 sachet of Enterosgel® 3 times a day

If you don't have loose stool or have it just once a day:

1 tablespoon or 1 sachet of Enterosgel® 1-2 times a day

Days 6 and 7:

If you have loose stool more than once a day:

1 tablespoon or 1 sachet of Enterosgel® 3 times a day

If you don't have loose stool or have it just once a day:

Stop taking Enterosgel®

ENT02UK

Enterosgel® use instructions v.1.0

12/10/2016

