APPENDIX C: PATIENT DIARIES

Randomised, multi-centre study to assess efficacy, tolerability and safety of Enterosgel® in treatment of acute diarrhoea in adults

PATIENT DIARY (CONTROL GROUP)

Patient Identifier:	Date:	_
DIARRHOEA		

After every bowel movement, please write down the time of the movement below. Please also check one option that best describes the consistency of the stool (by placing a check mark or a cross in the relevant column).

	Time (for example 6.15 am)	Liquid/ Watery/ Loose	Soft	Firm/ Solid
Morning 6 am-12 pm				
Day 12 pm-6 pm				
Evening 5 pm-12 am				
Night 12 am-6 am				

ENT02UK

Patient Diary Control Group v.1.0

09/10/2016

SYMPTOMS					
Please circle experience a		ns you have	experienced today, or "	None" if you di	d not
None	Nausea	Vomiting	Abdominal pain	Other	
lf other, pleas	se describe:				
Body tempe	rature in the	e morning: _	°C Body tempera	ature in the eve	ening:°C
TREATMENT	rs				
Every time af	ter taking yo	our oral rehy	dration treatment, pleas	se write down tl	ne time below.
	nn and des		ou took by placing a cro experienced any side ef		
	Time (for examp	le 6.15 am)	Describe any side effe complications	cts or	
Morning 6 am-12 pm					
Day 12 pm-6 pm					
Evening 6 pm-12 am					
Night 12 am-6 am					
Please list h	ere if you h	nave used ar	ny other medication(s) for your diar	rhoea today:
ENT02UK		Patient	Diary Control Group v.1.0	0	09/10/2016

PATIENT DIARY (ENTEROSGEL® GROUP)

Patient Identifier:	Date:	
DIARRHOEA		

After every bowel movement, please write down the time of the movement below. Please also check one option that best describes the consistency of the stool (by placing a check mark or a cross in the relevant column).

	Time (for example 6.15 am)	Liquid/ Watery/ Loose	Soft	Firm/ Solid
Morning 6 am-12 pm				
Day 12 pm-6 pm				
12 piii-o piii				
Evening 6 pm-12 am				
Night 12 am-6 am				

ENT02UK

Patient Diary Enterosgel® Group v.1.0

09/10/2016

SYMPTOMS					
Please circle experience a		s you have	experienced t	oday, or "No	ne" if you did not
None	Nausea	Vomiting	Abdomi	nal pain	Other
If other, pleas	se describe:				
Body tempe	r ature in the	morning: _	°C Body	/ temperatui	re in the evening:°C
TREATMENT	rs				
Every time af	ter taking dia	arrhoea trea	atment, please	write down t	he time below.
	mn and desc				or check mark in the ts which you think could be
	Time (for example	e 6.15 am)	Enterosgel®	Oral rehydration treatment	Describe any side effects or complications
Morning					

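### Stool frequency (secondary outcome 3) is averaged over a window that ends at the primary event, so the arm comparison is confounded with duration and can mislead in size and even in direction

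*Protocol*

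**What the plan says.** Section 2.2 sets out as a secondary objective "To investigate the impact of Enterosgel® on" several measures, the first of which (2a) is stool frequency. Section 3.2.2 turns this into outcome 3: "Stool frequency defined as average number of stools/day from randomisation to first soft or firm stool".

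The event that ends the averaging is the one that defines the primary outcome in section 3.2.1: "Duration of diarrhoea defined as time (hours) from randomisation to first nonwatery stool (soft or firm". Section 8.1 powers the trial on moving that event: "In order to detect an average decrease of 1 day in the duration of diarrhoea".

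Section 8.2 has continuous secondary outcomes "compared using a t-test or Mann Whitney test for continuous data", with p<0.05 as the criterion. It makes no allowance for unequal observation windows.

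The data for a common window are already collected. Section 6 says "Patients should fill in the patient diary daily from Day 0 until end of Day 7", and the diary in Appendix C instructs "After every bowel movement, please write down the time of the movement below", with a consistency box for each stool. The protocol does not say whether the closing soft or firm stool counts in the numerator, or how part-days enter the denominator.

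**The concern.** A rate compared between randomised arms should be measured over a period that treatment cannot alter. Here the length of the period is itself an outcome. If Enterosgel® works as hoped, its patients contribute shorter windows, taken from the earliest part of the episode. Control patients contribute longer windows that run into later days. The fall in stool number after recovery, which is a large part of what reducing stool frequency would mean, is left out for everyone.

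Neither a t-test nor a Mann-Whitney test corrects for this. The trial could shorten the illness and still report no difference, or a higher stool frequency, on objective 2a. The reader could not tell whether that reflected the treatment or the definition.

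**Working it through.** **The plan's own figure.** The protocol gives no figure for stool frequency. Its primary sample size reproduces with SD 1.3 d, difference 1 d, 90% power and 5% two-sided (sidedness is not stated): n = 2 × 1.3² × (1.960 + 1.282)² / 1² = 35.5, so 36 per group. Then 36/0.70 = 51.4, so 52 per group and 104 in all. This point does not touch that calculation.

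**One patient, three readings.** Patient A's first stool after randomisation is soft and comes at 4 h. Patient B has 4 watery stools a day for three days, then a soft stool at 72 h.

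- Closing stool counted, fractional days: A = 1/(4/24) = 6.0; B = 13/3 = 4.3.
- Closing stool excluded: A = 0; B = 12/3 = 4.0.
- Counted, per started day: A = 1/1 = 1.0; B = 13/3 = 4.3.
- Fixed 0-72 h, with A assumed to pass 1.2 stools/day after recovery: A = (1 + 1.2 × 68/24)/3 = 4.4/3 = 1.5; B = 13/3 = 4.3.

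Which patient scores higher depends on a rule that the definition leaves open. For a window of T days, counting the closing stool adds exactly 1/T to the score: 0.77 at T = 1.3 d but 0.43 at T = 2.3 d. The faster arm is penalised more.

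**Simulation with a constant rate while ill.** Inputs from section 8.1 are the 1-day difference and SD 1.3 d. Assumed, because the protocol gives none, are 4 stools/day while ill in both arms, mean durations of 2.3 vs 1.3 d or 3 vs 2 d, and a lower stool rate after recovery. Results are mean stools/day, Control vs Interventional.

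At 2.3 vs 1.3 d:
- counted, fractional days: 4.3 vs 5.1 (4.2 vs 4.8 under another assumption about stool spacing)
- excluded: 3.75 vs 3.4
- counted, per started day: 3.5 vs 3.0
- fixed 72 h: 3.3 vs 2.6

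At 3 vs 2 d:
- counted, fractional days: 4.2 vs 4.4
- fixed 72 h: 3.7 vs 3.1

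The result also depends on how soon the first soft stool follows recovery. If that gap is stretched to a rate of 1.2/day, the counted version at 2.3 vs 1.3 d becomes 3.65 vs 3.68, almost no difference.

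**Simulation with other patterns.** A second set of runs assumed control means of 2.5 or 3.5 d, about 5 stools/day at randomisation, 1.5/day after recovery and a 1-day benefit with no other effect. Differences are Interventional minus Control, closing stool counted unless stated.

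- Frequency falls with time: +0.26 stools/day, the wrong direction. The Interventional mean is higher in 74-80% of trials of 36 per arm and significantly higher in about 10%. With the closing stool excluded: +0.06 to +0.12.
- Constant frequency until recovery: -0.15 to -0.20.
- Decline scaled to each patient's own duration: -0.04 to -0.07.
- Sicker patients have both more stools and longer illness (correlation 0.5): -0.09 to -0.22.

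Fixed windows favoured the faster arm in every scenario. Under falling frequency, where the planned outcome had the wrong sign, watery stools over the first 3 days differed by -0.62 and -0.43 stools/day at control means of 2.5 and 3.5 d. All stools over Days 0-7 differed by -0.13 and -0.08.

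**Why falling frequency matters.** Take 6, 4, 3, 2 and 1 stools on successive days. Recovery after 1, 2, 3, 4 or 5 days scores 6.0, 5.0, 4.3, 3.75 or 3.2 under the planned definition, so quicker recovery scores worse. Over a fixed 7 days with 1 stool/day after recovery, the scores are 1.7, 2.1, 2.4, 2.6 and 2.6.

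**The case against.** Stool frequency while ill is a coherent descriptive measure of severity. The benefit in duration is already captured by the primary outcome and by secondary outcomes 1 and 2, so the trial as a whole does not ignore what happens after recovery. Whether the closing stool counts, how part-days are handled and what is done for patients unresolved at Day 7 are derivation rules that a statistical analysis plan may settle. Under two natural choices (closing stool excluded, or stools per started day) the constant-rate runs show a benefit. All of this stands. It does not remove the treatment-dependent window: under falling frequency the sign was wrong even with the closing stool excluded.

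Three stronger readings are tempting and are not supported.

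- A reader might infer that the quickest recoverers necessarily score highest. That needs falling frequency or a counted closing stool. When sicker patients had both more stools and longer illness, at a control mean of 2.5 d, the fastest quartile had the lowest median (3.7, against 4.8 in the slowest).
- A reader might infer that an effective treatment will often look significantly worse. That frequency depends heavily on assumptions. At 3 vs 2 d, with the closing stool counted, it was between 3% and about 7% of trials.
- A reader might extend the point to the primary outcome, because Appendix A tells participants to stop "if you did not have any bowel movements for 2 days at any stage of the study" and such stool-free time counts towards the primary duration. That instruction is a conditional precaution and predicts no frequency. Secondary outcome 1, time to last watery stool, already gives a view of duration that leaves such time out when no watery stool follows.

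**Conclusion.** The point holds for one secondary outcome. Outcome 3 compares the arms over windows that treatment is meant to change, so its result mixes frequency with duration and cannot be relied on to answer objective 2a. For a treatment that only shortens illness by 1 day, the difference in the runs at an assumed 4 stools/day while ill ranged from about half a stool per day in favour of treatment (3.5 vs 3.0) to about 0.8 against it (4.3 vs 5.1). The adverse result shrinks to 0.2 (4.2 vs 4.4) at 3 vs 2 d.

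These sizes rest on assumed stool rates, mean durations and counting rules, none of which the protocol supplies. They show that the direction is undetermined, not that it will be wrong. The advantage of the fixed window rests on the milder assumption that stools are less frequent after recovery than during illness. The change should be made, since objective 2a is a stated objective with a formal test. The primary outcome and the sample size of 104 are not affected.

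**What to change.** In section 3.2.2, define outcome 3 as the number of stools per 24 h, and separately of watery stools (the diary's liquid/watery/loose column), over a fixed window from randomisation that is the same for every randomised patient whenever the first soft or firm stool occurs. 0-72 h is a reasonable example and sits close to the Day 3 point already used in outcome 2.

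Keep the present measure, if wanted, as a descriptive summary of frequency while ill without a between-arm test, and state whether the closing stool counts and how part-days are treated.

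The cost is wording only. The diary already times every stool to the end of Day 7, so no new data, calls or patients are needed. The downside is small: a fixed-window count overlaps in part with duration and no longer isolates frequency while ill, which is why the present measure is worth keeping as description. Patients who withdraw before 72 h will have incomplete windows and fall under the missing-data approach of section 8.2.

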3.2.3 Exploratory Outcome(s)

Percentage of patients developing Irritable Bowel Syndrome (IBS) symptoms or other chronic gastrointestinal conditions or acute diarrhoea following the acute diarrhoea episode (within 6 to 20 months).

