1 BACKGROUND

Approximately 20% of the UK population develop infectious intestinal disease each year (1). It is characterized by the sudden onset of diarrhoea, with or without vomiting. Other symptoms may include nausea, fever and abdominal pain. Most cases are due to an enteric virus, such as the rotavirus, but some are caused by bacterial or protozoal infections (2). The illness usually resolves without treatment within days; however, symptoms are unpleasant and can affect the whole family. Severe diarrhoea can quickly cause dehydration, which may be life threatening if not treated quickly.

Although intestinal infections are often managed at home without seeking professional advice, they still pose a significant burden on health service resources and the economy with many patients and parents missing time from work and seeking advice from healthcare professionals in primary or secondary care (1,3,4). For example, approximately 10% of children younger than 5 years present to healthcare services with gastroenteritis each year (5) and in the UK diarrhoeal illness has been reported to account for 16% of clinical presentations to a major paediatric emergency department (6). While there appears to be a lack of recent data on the economic and healthcare burden of intestinal infections, data from mid 1990s suggested that around 1 in 5 people in England suffered from infectious intestinal disease every year, with around 35,000 hospital admissions and 300 deaths annually and an estimated annual cost to the nation of £0.75 billion (4,7). The treatments recommended for acute diarrhoea by The National Institute for Health and Care Excellence (NICE) guidance are fluid management and nutritional management (1,3). However, standard rehydration management does not reduce the duration of diarrhoea (8) and the challenge of treating diarrhoea itself remains. There is a need for novel treatments, which can decrease the duration of illness and reduce attendances to primary care or emergency departments.

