2.3 EXPLORATORY OBJECTIVE(S)

The exploratory objective of this study is to investigate the incidence of Irritable Bowel Syndrome (IBS) -related symptoms and gastrointestinal conditions following an acute diarrhoea episode in the two treatment groups. Our hypothesis is that the use of intestinal adsorbents during an acute diarrhoea episode, could potentially reduce the likelihood that more persistent intestinal problems develop after an acute episode. The data from this study will be used as pilot data to help design larger studies in the future, with the aim of understanding the mechanisms of chronic intestinal conditions such as IBS.

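### Section 3.2.3 pools any later acute diarrhoea with IBS symptoms and chronic conditions, which dilutes the persistent-problem rate that section 2.3 is about

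*Protocol*

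**What the plan says.** Protocol section 3.2.3 gives one exploratory outcome, a single percentage with three parts joined by 'or': "Percentage of patients developing Irritable Bowel Syndrome (IBS) symptoms or other chronic gastrointestinal conditions or acute diarrhoea following the acute diarrhoea episode". The window is "within 6 to 20 months". The wording does not say that the parts will be shown separately.

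Protocol section 2.3 sets the objective: to "investigate the incidence of Irritable Bowel Syndrome (IBS) -related symptoms and gastrointestinal conditions following an acute diarrhoea episode in the two treatment groups". The hypothesis is that adsorbent use during the episode "could potentially reduce the likelihood that more persistent intestinal problems develop after an acute episode". On use of the results it says: "The data from this study will be used as pilot data to help design larger studies in the future". The sentence ends by naming chronic intestinal conditions, with IBS as the example, as what those studies should explain. In section 2.3 acute diarrhoea appears only as the index episode.

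Protocol section 1 supplies the only background rate: "Approximately 20% of the UK population develop infectious intestinal disease each year". The protocol states no expected IBS or chronic-condition rate, effect size or power for this outcome.

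**The concern.** A patient who has a further bout of acute diarrhoea months later, and nothing else, is an event under section 3.2.3. That patient says little about whether persistent problems became less likely. Section 1 describes acute intestinal infection as common and as usually clearing up within days, and no section gives a reason why a device taken for 5 to 7 days should prevent a later episode. If such episodes are equally frequent in both arms, they raise both percentages and move the ratio between them towards 1.

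What is at stake is the use the protocol itself names. A pilot on chronic sequelae is useful mainly for the event rate it supplies. The pooled percentage is not an incidence of IBS or chronic conditions, and it depends on how long each patient was followed. The primary and secondary outcomes are not touched.

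**Working it through.** **The plan's own figure.** None is given for this outcome. The primary sample size in section 8.1 ("we assumed a standard deviation for the duration of diarrhoea of 1.3 days"; "detect an average decrease of 1 day in the duration of diarrhoea"; 90% power, 5% level) reproduces with a two-sided test: 2 × (1.960 + 1.282)² × 1.3² / 1² = 35.5, so 36 per group; 36 / 0.70 = 51.4, so 52 per group and 104 in total. It does not bear on the point except to fix 52 per arm.

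**Inputs.**
- Background rate: 20% per year (section 1). Assumed to apply to these patients, at a constant rate, independently of treatment and of IBS/chronic events.
- Follow-up: 6 to 20 months (section 3.2.3), counted from the index episode.
- IBS/chronic rate p: not in the documents. Assumed 10% or 20% in controls, halved by treatment.

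**Formulas.**
- Background risk: b = 1 − 0.8^(months/12).
- Composite risk: 1 − (1 − p)(1 − b).
- Share of control events that are acute diarrhoea only: b(1 − p) / [p + b(1 − p)].

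**Example, 20 months, 10% versus 5%.** b = 1 − 0.8^(20/12) = 0.311. Control: 1 − 0.90 × 0.689 = 0.380. Treated: 1 − 0.95 × 0.689 = 0.345. Ratio 0.345 / 0.380 = 0.91. Acute-only share: 0.311 × 0.90 / 0.380 = 0.74.

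| Months | b | Composite at 10% vs 5% | RR | Acute-only share | Composite at 20% vs 10% | RR | Acute-only share |
|---|---|---|---|---|---|---|---|
| 6 | 10.6% | 19.5% vs 15.0% | 0.77 | 49% | 28.4% vs 19.5% | 0.69 | 30% |
| 12 | 20.0% | 28.0% vs 24.0% | 0.86 | 64% | 36.0% vs 28.0% | 0.78 | 44% |
| 20 | 31.1% | 38.0% vs 34.5% | 0.91 | 74% | 44.8% vs 38.0% | 0.85 | 55% |

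The true ratio is 0.50 throughout. The risk difference shrinks by the factor 1 − b: at 10% versus 5% it falls from 5.0 points to 4.5, 4.0 and 3.4. If the window means events between month 6 and month 20 only (14 months), b is 22.9%, the ratio at 10% versus 5% is 0.87 and the acute-only share is 67%, inside the range above.

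**When acute-only events are the majority.** The share exceeds one half when b(1 − p) > p, that is p < b / (1 + b). This gives 0.106 / 1.106 = 9.5% at 6 months, 0.20 / 1.20 = 16.7% at 12 and 0.311 / 1.311 = 23.7% at 20.

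**Power with 52 per arm, two-sided 5%, no losses.** At 10% versus 5%: 16% without acute diarrhoea; 8.7%, 6.7% and 5.5% with it at 6, 12 and 20 months. At 20% versus 10%: 30% without; 18.5%, 13.8% and 10.6% with it.

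**Size of a later trial with 80% power, if it used the same outcome.** n per arm = [1.960√(2p̄(1 − p̄)) + 0.842√(p₁(1 − p₁) + p₂(1 − p₂))]² / (p₁ − p₂)², where p₁ and p₂ are the two arms' risks and p̄ is their mean. At 10% versus 5%: 435 without acute diarrhoea; 1,120, 1,887 and 3,051 with it. At 20% versus 10%: 199 without; 357, 533 and 801 with it.

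**The case against.** Much of the case on the other side stands, and it limits the point.

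- A reader might infer that sections 2.3 and 3.2.3 flatly contradict each other. They do not. The objective sentence speaks of gastrointestinal conditions without restricting them to chronic ones, and acute diarrhoea is such a condition. The tension is with the hypothesis and the closing aim.
- A reader might infer that acute episodes would dominate the outcome and hide an IBS effect. The first depends on an IBS/chronic rate that the protocol does not give: at 6 months acute-only events are a minority for any rate above about 9.5%. As to the second, 52 per arm has only 16-30% power for a halving from 10% or 20% even without acute diarrhoea, so such an effect would usually be missed anyway.
- A reader might infer that every later episode is a fresh infection which the device could not affect. The protocol does not say so. The outcome wording also admits relapse or recurrence, which is a reasonable thing to record in a pilot. If treatment reduced recurrences, the dilution would be smaller.
- The 20% is for the whole UK population and all infectious intestinal disease, much of it managed at home. The rate in these adults, and the part they would report months later, may differ.
- The outcome is exploratory, with no decision attached. The inflated sizes for a later trial arise only if someone plans on the pooled figure and ignores its parts, which the protocol does not propose.
- A statistical analysis plan, not among the documents, might show each part.

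The last point does not remove the concern. Followed as written, the protocol's outcome is one pooled percentage. Nor does low power excuse it, because the stated purpose is pilot information, and for that the rate itself matters.

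**Conclusion.** The point holds as one of dilution. The outcome in section 3.2.3 is wider than the hypothesis and aim in section 2.3, and its pooled percentage would not give the IBS/chronic incidence that the pilot purpose calls for. The direction is certain if later acute episodes occur independently of treatment. The size is conditional on the 20% yearly rate applying at a constant level, and on an IBS/chronic rate for which 10% and 20% are only illustrations. Background risk also differs about threefold between 6 and 20 months (31.1 / 10.6 = 2.9), so the pooled figure mixes patients with quite different exposure. The documents do not support saying more: neither that acute diarrhoea must dominate, nor that it would conceal an effect this trial could otherwise show. For an exploratory outcome this is worth correcting, but it does not affect the trial's main conclusions.

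**What to change.** In Protocol section 3.2.3, define the exploratory outcome as the percentage of patients with IBS symptoms or other chronic gastrointestinal conditions over the stated window. Report new or recurrent acute diarrhoea as a separate descriptive percentage, so that nothing is lost.

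The cost is a line of protocol wording and one extra table row. No further patients are needed, and no further data provided the follow-up contact records which kind of event occurred. The small downside is fewer events, and so a less precise percentage, in the main exploratory outcome. In return, the figure carried into later planning is the one section 2.3 asks about.
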